We request consent to access clinical screening records, NCSP records, and hrHPV vaccination records.

Currently the National Cervical Screening Programme Register (NCSPR) is not structured to record an hrHPV screening test. However, the result and follow up recommendation following an hrHPV test will be shared with the NCSP.

Patients will be asked if they would provide consent to be approached to take part in online survey or structured phone interview about hrHPV screening (consent is optional and not a requirement to be in the study).

Screening tests

Please see flow charts in Appendix 6.

Most patients enrolling in the study will have 3 options regarding their screening test:

1. Vaginal hrHPV self-test at home or other suitable location
2. Vaginal hrHPV self-test at practice
3. Clinician-taken cervical sample (liquid-based cytology specimen) which will be tested for hrHPV.

In exception to this, patients who have been under follow up of a previous abnormality and according to agreed guidelines require cervical cytology in addition to hrHPV testing. They will be advised to have a clinician taken cervical sample, this will be tested for hrHPV and cytology. Patients who report symptoms will also be recommended to undergo a cervical sample that will be tested for hrHPV and cytology in addition to any other investigations that are deemed necessary by the care provider.

Vaginal hrHPV self-tests will be taken utilising a dry floq swab inserted in the vagina and transported in a sterile sealed container.

Cervical hrHPV tests will be taken under direct visualisation by an accredited cervical screener (smear-taker) using a cervibroom or equivalent and placed in liquid-based cytology medium.

The hrHPV test will be performed utilising an accredited laboratory and an hrHPV assay validated for cervical hrHPV screening.

A modified clearly distinguishable study laboratory request form will be utilised.

Tests will be logged in the practice or at the central study site.

A clinician responsible for the screen result will be designated.

Vaginal hrHPV self-test at home

If a participant indicates this choice, they will be given or sent by mail or courier a sample pack containing instructions consent form, a floq swab, sterile container and prepaid courier pack.

The participant will also have a phone number of the lead nurse from the practice and the study nurse and contact hours to ask any questions.

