These occurrences will be logged in the practice where possible and identified from the NCSPR on completion of the study.

If a patient undergoes an off-study cytology test they will receive no further invitations for screening as part of the study.

Cytology triage (risk stratification)

As the incidence of hrHPV is higher than the incidence of CIN2 + and the risk of CIN2 or greater varies by the hrHPV type and cervical cytology findings, in most hrHPV screening programs, cytology is used to triage patients prior to colposcopy referral.

Reflex cytology process

If the sample has been performed as a clinician-based cervical sample, a liquid-based cytology examination will be performed in the reporting laboratory in the routine manner on the same specimen without further request. Reporting will be as per modified Bethesda (NZ) as per NCSP

recommendations. The pathologist's recommendation will be made as per NCSP guidelines, but it will also be noted that the patient is participating in the pilot study and study recommendations may vary from this. The report will be forwarded to the NCSP.

If a self-test hrHPV has been performed and hrHPV is detected, the patient will be recommended to undergo a clinician-taken cervical sample at their practice. This sample can be taken by any cervical screener. The cervical cytology will be performed in a routine manner at an accredited laboratory. The sample will be marked that the patient is taking part in the pilot study and the result of the hrHPV test. Reporting will be as above.

A patient with HPV16/18 will be referred directly to colposcopy. Because cytology is considered helpful to the colposcopist and to exclude other pathology a cervical cytology test is recommended for these participants, however it is not required and should not create a barrier for the participant. Patients who are experiencing symptoms should undergo a speculum examination cervical cytology and investigations as indicated.

Patients may choose to have the reflex cytology done at a non-participating practice. This is discouraged as it will make correlation of results more difficult. The cytology will then be performed and reported as per NCSP guidelines. The reporting pathologist may not be aware of prior hrHPV results and recommendation for referral will be made on the basis of cytology.

Patients with prior cervical abnormalities (Test of Cure)

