In order to align with current NCSP practices, in terms of database requirements and automatic recall procedures, all patients in the clinician-taken sample group will have a cytology assessment of the sample they have already given, thus, do not need to return for a follow up cervical screen. The two groups, therefore, cannot be directly compared in terms of failure to return for follow up. In addition, as the clinician-taken and self-sample groups are self-selected they will be different and, hence, outcomes from the two groups will be recorded but cannot be directly compared.

Due to the relatively small size of this study and the unlikely outcome of a high-grade cervical abnormality, outcomes related to colposcopy referral will lack the power for stratification. However, the choice of screening method may usefully be able to be stratified.

Transfer of data and patient care to the NCSP.

The NCSPR will be informed of all patients participating in the study.

As the NCSPR is not currently able to manage the results of hrHPV screening this information will be overseen by the study team. The study team will act in place of the NCSPR to provide reminders to the practices when patients are overdue further investigations or repeat testing and to ensure management recommendations are correct. Following colposcopy or on completion of the study when the NCSPR is able to manage these patients' information they will be referred back to the NCSPR

Results of all cytology tests and hrHPV tests and colposcopy records will automatically be referred to the NCSPR. The study team will follow all patients to the end of the study to ensure patients who require colposcopy have been seen.

At completion of the study enrolled patients will fall under the following categories.

- Normal screen, next routine screen to be performed at the normal screening interval (5 years)
- Normal screen but because of previous abnormality follow up recommended in 12 months
- Abnormal screen referred to colposcopy attended follow up dictated by colposcopist and referred back to NCSP

- Abnormal screen colposcopy recommended lost to follow up/colposcopy declined
- Abnormal screen follow-up cytology advised but declined/lost to follow up
- Abnormal screen cytology performed follow up in 12 months recommended

This information will be shared with the NCSP (as far as possible in a manner that is suitable to the NCSP) and patients will be discharged to GP practice and NCSP

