Participants who withdraw consent for the study, who transfer their care to a non-participating practice or who are lost to follow up will be regarded as off study. Every reasonable effort will be made to ensure they are aware of their test result and the subsequent recommendation, and that this information is shared with the appropriate health professionals that are involved. The NCSPR will also be informed.

Financial considerations

The NCSP has indicated it will provide the following support:

- Funded colposcopy in public hospital as per agreed referral criteria
- The laboratory cost of cytology tests
- The financial support of the study grant
- Funding to support screening activities within usual PHO funding

The cost to practices not covered by the study grant will therefore be met by the patient. However, it is unethical for a patient to be charged more for a study cervical screening procedure than for a current NZ standard of care cervical cytology.

The study payment to GP clinics is to cover the time and resources required to provide study information for full informed consent, this cost must not be passed on to patients. The payment also covers the time required for clinic staff to provide data for the University of Otago Redcap database (clinics in the Wellington and Canterbury regions only; in Whanganui this will be conducted by the PHO (Whanganui Regional Health Network) on their behalf).

As the costs of administration and post is covered by the grant, we anticipate that participants taking the self-test at home would only involve the cost of the initial study visit, and would include education on how to undertake an hrHPV self-test.

We anticipate that participants having an hrHPV self-test in the clinic with the support of a nurse may have a facility charge similar to the cost of a nurse visit.

Participants requesting a clinician-taken cervical hrHPV test will have a charge identical for a current NZ standard of care cervical cytology.

Participants who have a positive cytology test following a positive hrHPV screen should not have a total cost greater than for a current NZ standard of care cervical cytology. This cost should be subsidised from elsewhere (other screening activities or screening support funds).

Participants who would normally be eligible for a free cervical cytology screen in that practice should be offered a free hrHPV screen (and, if required, cervical cytology).

Ethical Considerations

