Appendix 1 *Data Management Plan (see separate document)*

Appendix 2 Safety and quality assurance plan

Introduction

This study is performed to determine the impact of implementation of hrHPV testing into the NCSP. The aim of screening is to prevent cervical cancer by the identification and treatment of the precursors to cervical cancer. While the NCSP has been a highly successful public health intervention, screening has its limitations and for individual screening failure can occur, this may be due to the inherent weaknesses of the test, diagnostic and treatment pathways, or failure of the process to be carried out correctly. It is well documented that the major cause of screening failure is non-engagement with the screening program, however, failure of the screening test to detect an abnormality and failure of the diagnostic and treatment pathway are also associated with a significant number of cancer occurrences. In addition, there are a number of service delivery interactions that may significantly affect the quality of a patient's experience which may in turn have an impact on future participation. It is well documented that the impact of these failures is inequitable.

The introduction of hrHPV testing will be associated with an increased sensitivity of the screening test and offers greater accessibility of the test and hence will improve the safety of the program. However, the change in procedures may increase, at least temporarily, the possibility of procedural or administrative errors. It is therefore important to monitor patient safety aspects of this study. This will be done by reporting adverse events, site visits, and auditing of data against source documents.

Identified risks

Major risks

Failure to detect significant abnormality (false negative test)

Patient given wrong result

Patient given inappropriate advice

Patient not informed regarding a positive result

Colposcopy for high grade cytology or HPV 16/18 not attended within 3 months

Inequity associated with participation

Other risks

Eligible patients not invited

Minimum invitation requirements not met

Patient positive for other hrHPV (i.e., non-HPV16/18) does not attend for cytology

Patient with other hrHPV (i.e., non-HPV16/18) does not attend for colposcopy

Serious adverse event reporting

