As the NCSPR is not currently able to manage the results of hrHPV screening this information will be overseen by the study team. The study team will act in place of the NCSPR to provide reminders to the practices when patients are overdue further investigations or repeat testing and to ensure management recommendations are correct. Following colposcopy or on completion of the study when the NCSPR is able to manage these patients information they will be referred back to the NCSPR.

To ensure the clinical safety of participants. The redcap database will generate reminders to the general practice and to the study management team to ensure that critical parts of the patient care episode are completed. For example, informing patients of results, having a cervical cytology test and attending colposcopy within pre-determined time frames. While the general practice team will hold clinical responsibility for these actions the study management team will act as a safety net and prompt the clinicians involved. Thus, the database and the study management team are offering a greater degree of safety than the NCR, which at this point is unable to process hrHPV screening tests.

In addition, for all patients with an abnormal hrHPV test the recommendation recorded on the database will be cross checked against their result and cervical screening history to ensure this is consistent with guideline. Where this is not correct the inconsistency will be investigated by the study team and the provider.

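### A participant who moves to a non-participating practice goes off study even with a positive hrHPV result unresolved, although the protocol undertakes to follow all patients

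*Protocol*

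**What the plan says.** The Methods section, the section on transfer of data and patient care to the NCSP, and Appendix 2 (Quality assurance) all say that the study team stands in for the NCSPR, because the register cannot at present manage hrHPV screening results. The consent section puts it this way: "Currently the National Cervical Screening Programme Register (NCSPR) is not structured to record an hrHPV screening test". Appendix 2 claims that the database and study team give more safety than "the NCR, which at this point is unable to process hrHPV screening tests".

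Standing in for the register means reminding practices of overdue steps and checking that management is right. Appendix 2 adds that "for all patients with an abnormal hrHPV test the recommendation recorded on the database will be cross checked against their result" and screening history.

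The transfer section sets the extent of this duty: "The study team will follow all patients to the end of the study to ensure patients who require colposcopy have been seen". Patients return to the register "Following colposcopy or on completion of the study when the NCSPR is able to manage" their information.

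A little further on, the same section defines who leaves. Along with those who withdraw consent, participants "who transfer their care to a non-participating practice or who are lost to follow up will be regarded as off study". For all of these, reasonable efforts are to be made so that the person knows the result and what is recommended, and so that the clinicians involved know it too. The NCSPR is informed as well.

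**The concern.** The undertaking to follow everyone carries no stated exception. The exit rule treats someone who has only changed practice like someone who has withdrawn consent, whatever their hrHPV result and whether or not a diagnostic step is pending.

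For a person with a negative result little is at stake. For a person with a positive result awaiting cytology or colposcopy, transfer appears to end the study's tracking before the end points the protocol sets, while the register cannot yet take the job over. Appendix 2 counts this among the major risks: "Colposcopy for high grade cytology or HPV 16/18 not attended within 3 months". It presents the study's reminders and checks as a safeguard for such steps.

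The matter is participant safety during follow-up. It does not bear on the analysis.

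**Working it through.** No arithmetic settles this, so the provisions are set side by side.

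1. **Who is to be followed.** All patients, to the end of the study, for the stated purpose of seeing that those needing colposcopy get it (transfer section).
2. **When the study's role ends.** After colposcopy, or at study completion once the register can manage the information (transfer section).
3. **Who leaves sooner.** Those who withdraw consent, move to a non-participating practice or are lost to follow-up (same section). The rule names no hrHPV result and no outstanding step.
4. **What is kept for someone who transfers.** The result and recommendation go to the person and the clinicians involved, and the register is informed. Clinical responsibility lies with general practice in any case (Appendix 2), and study tracking is additional to ordinary practice recall (Methods).
5. **What is not stated to continue.** The overdue reminders, and the check of the recorded recommendation against the hrHPV result and history. Nothing is named in their place.
6. **Comparison with someone who stays.** Under the heading on patients who do not attend for recommended cytology or colposcopy, the NCSP is notified of non-attendance. For someone who transfers and then does not attend, the protocol describes no check that would reveal it. A willing participant who moves therefore seems to be watched less closely than one who stays and declines.
7. **Whether continued tracking is feasible.** Consent already covers access to NCSP records (consent section). The NCSPR is a named data source (Data management). Cytology, hrHPV and colposcopy results go to it automatically (transfer section). Cytology done off study is already to be identified from it (Off-study cytology tests).

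**Size.** The number affected would be:

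affected = (hrHPV-positive participants with a step outstanding) × (proportion who transfer before it is done)

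The protocol gives no value for the second factor, so no number follows.

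**The case against.** The strongest reply is that the exit rule is a specific exception to a general promise. It stands in the same section, and the word all must already exclude people who withdraw consent, so transfers can be read the same way. That is a fair reading, and it means the two sentences need not be called a flat contradiction. It does not explain why a person who still consents should be grouped with one who does not.

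The handover duty is also real and has no stated time limit. The term off study is not defined, so the view that it ends tracking is an inference, though a natural one in a section about handing over care.

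A reader might infer several stronger things that the documents do not support:

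- **That telling the register early breaks the hand-back rule.** It does not. The register is informed of all participants and receives results automatically. The end points govern referral back, not informing.
- **That the new practice's recall is the only protection left.** The person and the clinicians have been told, and colposcopy services issue their own invitations. What may go is a supplementary layer.
- **That referral would be missed because cytology is read without the hrHPV result.** The protocol does say of reflex cytology at a non-participating practice: "The reporting pathologist may not be aware of prior hrHPV results and recommendation for referral will be made on the basis of cytology". That sentence concerns a patient's choice of where to have the sample taken, not a transfer in which the hrHPV result must be handed on. Appendix 3's 24.4% risk of CIN2+ for HPV 16 with normal cytology (49 of 201) is a poor measure here, because HPV 16/18 goes straight to colposcopy and cytology is not required.

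**Conclusion.** The point holds as a minor one. The protocol promises to follow all patients, then takes participants who transfer off study without an exception for an unresolved positive result. What appears to be lost for them is the supplementary tracking and recommendation check, which the register cannot yet supply. This rests on reading off study as ending those activities, which the protocol does not say outright.

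The number affected is unknown and probably small. It would be tempting to quote whole-group totals: about 132 colposcopy referrals (44 per 1,000 from Appendix 4, times 3,000), or 216 to 252 positive self-tests (12% of 1,800 to 2,100, from Statistical Considerations). These count everyone who will have a step to complete, not those who transfer before completing it, and the second includes HPV 16/18 positives who do not need cytology. Neither should stand as the size of this problem.

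The change is still worth making, because it closes a gap for people who have not asked to leave and the means to do so are already in the protocol.

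**What to change.** In the off-study paragraph of the transfer section, separate transfer from withdrawal and loss to follow-up, and leave the wording for the last two as it is. Then provide that:

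- an hrHPV-positive participant who transfers without withdrawing consent, with cytology or colposcopy outstanding, stays on the study team's tracking list until colposcopy or study completion, the end points the section already uses;
- status is read from NCSPR cytology and colposcopy records, and Appendix 2's check of the recommendation against the hrHPV result is kept;
- if no step is recorded at 3 months, the interval Appendix 2 already uses for missed cytology and colposcopy, the NCSP is notified as it is for non-attenders;
- a transferred category is added to the section's list of end-of-study categories.

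The existing duty to share the result and recommendation stays.

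The cost is a few sentences and one record lookup per transferred positive participant. No duty falls on non-participating practices. The limit should be stated openly: this restores detection and notification, not the reminders that participating practices receive. Reading cytology and colposcopy from the register does not conflict with its inability to manage hrHPV results, because the study holds those itself.

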Appendix 1 *Data Management Plan (see separate document)*

Appendix 2 Safety and quality assurance plan

Introduction

This study is performed to determine the impact of implementation of hrHPV testing into the NCSP. The aim of screening is to prevent cervical cancer by the identification and treatment of the precursors to cervical cancer. While the NCSP has been a highly successful public health intervention, screening has its limitations and for individual screening failure can occur, this may be due to the inherent weaknesses of the test, diagnostic and treatment pathways, or failure of the process to be carried out correctly. It is well documented that the major cause of screening failure is non-engagement with the screening program, however, failure of the screening test to detect an abnormality and failure of the diagnostic and treatment pathway are also associated with a significant number of cancer occurrences. In addition, there are a number of service delivery interactions that may significantly affect the quality of a patient's experience which may in turn have an impact on future participation. It is well documented that the impact of these failures is inequitable.

The introduction of hrHPV testing will be associated with an increased sensitivity of the screening test and offers greater accessibility of the test and hence will improve the safety of the program. However, the change in procedures may increase, at least temporarily, the possibility of procedural or administrative errors. It is therefore important to monitor patient safety aspects of this study. This will be done by reporting adverse events, site visits, and auditing of data against source documents.

Identified risks

Major risks

Failure to detect significant abnormality (false negative test)

Patient given wrong result

Patient given inappropriate advice

Patient not informed regarding a positive result

Colposcopy for high grade cytology or HPV 16/18 not attended within 3 months

Inequity associated with participation

Other risks

Eligible patients not invited

Minimum invitation requirements not met

Patient positive for other hrHPV (i.e., non-HPV16/18) does not attend for cytology

Patient with other hrHPV (i.e., non-HPV16/18) does not attend for colposcopy

Serious adverse event reporting

Serious adverse events will be reported to the study management team by filling out a Serious Adverse Event (SAE) report form and emailed within 7 days of the GP practice becoming aware of the event.

Serious Adverse Events include:

- Interval diagnosis of invasive cancer, CIN3, or AIS following a negative hrHPV test
- A screened person being given the wrong result
- A screened person being given the wrong advice following their screen (e.g., not referred to colposcopy or cytology when they should have been)
- A screened person not receiving the result of a positive test

Serious adverse events will be investigated as soon as possible by the study team and the relevant service provider to ensure similar errors do not occur and that there is no systemic case for this error.

The service provider will be responsible for the discussion of this adverse event with the person affected and their whanau and informing other agencies if appropriate. The study team will be responsible for informing the NCSP.

The following other adverse events will also be reported at completion of the study

- A person referred to colposcopy who does not attend within 3 months
- A person with other hrHPV who is recommended to have cervical cytology but who does not attend within 3 months

Site visits

Site visits will be performed either face to face or virtually by at least 1 member of the study management team, prior to commencing invitation to the study and within 3 months of commencing the study. Additional visits will be organised on request of the participating practice or if issues are perceived by the study management team.

The first visit is to ensure mechanisms of enrolment data management and clinical management of patients is understood by all members of the team. In addition, to ensure that systems are appropriate.

The second visit is to understand any issues of concern being encountered by the practice and to ensure ongoing participation of the practice team with screening and study protocols.

Further site visits may occur as required if areas of concern have been identified.

Audit

Prospectively-collected data will be collected in electronic case report forms (e-CRF) within 4 weeks of the event. 10% of data will be audited against source documents. If more than 10% of data is missing or incorrect, further in-depth audit will be undertaken.

Quality assurance

As the NCSPR is not currently able to manage the results of hrHPV screening this information will be overseen by the study team. The study team will act in place of the NCSPR to provide reminders to the practices when patients are overdue further investigations or repeat testing and to ensure management recommendations are correct. Following colposcopy or on completion of the study when the NCSPR is able to manage these patients information they will be referred back to the NCSPR.

To ensure the clinical safety of participants. The redcap database will generate reminders to the general practice and to the study management team to ensure that critical parts of the patient care episode are completed. For example, informing patients of results, having a cervical cytology test and attending colposcopy within pre-determined time frames. While the general practice team will hold clinical responsibility for these actions the study management team will act as a safety net and prompt the clinicians involved. Thus, the database and the study management team are offering a greater degree of safety than the NCR, which at this point is unable to process hrHPV screening tests.

In addition, for all patients with an abnormal hrHPV test the recommendation recorded on the database will be cross checked against their result and cervical screening history to ensure this is consistent with guideline. Where this is not correct the inconsistency will be investigated by the study team and the provider.

